[name]
 Mayo Clinic
 Division of Hematology
 Dept. of Internal Medicine
 [name]
 [name]
 [contact]
 [contact]
 [contact]

IND Sponsor Contact Information:

[name].,
 IGF Oncology,
 [name],
 [name]
 [contact]
 [contact]

Synopsis

Primary Objective:

The primary objective of this study is to determine the safety and tolerability of utilizing the insulin-like growth factor-1-methotrexate conjugate, 765IGF-MTX for the treatment of advanced, previously treated myelodysplastic syndrome (MDS), chronic myelomonocytic leukemia (CMML) and oligoblastic acute myelogenous leukemia (oligoblastic AML or O-AML), including determining the maximum tolerated dose (MTD).

Secondary Objective:

The secondary objective of this study is to determine the clinical benefit of 765IGF-MTX as measured by partial and complete remission rates, relapse-free survival, and overall survival in patients with advanced, previously treated MDS, CMML, or O-AML.

Patient Population:

[figure not shown]
- Diagnosis of MDS, CMML or O-AML that is refractory to or intolerant of standard therapy and is no longer likely to respond to such therapy
- Patient must have recovered from the acute toxic effects (\leq grade 1 CTCAE v.4.0) of previous anti-cancer treatment prior to study enrollment
- Age 18 years or older
- ECOG performance status 0, 1, or 2 (appendix III)

Study Design:

This pilot study will evaluate use of IGF-Methotrexate conjugate (765IGF-MTX) in patients with advanced, previously treated MDS, CMML and O-AML. 765IGF-MTX at a dose of 0.20 to 2.5 μ equivalents per kg is administered as an IV infusion over 1.5 hours on days 1, 8 and 15 of a 28 day cycle. Treatment continues until disease progression, as assessed after 2 cycles, unacceptable toxicity, or patient refusal. Assessment of response will be confirmed by bone marrow studies performed at the end of cycles 2, 4, and 6 (each +/- 3 days).

Once a final maximum tolerated dose level (MTD) is determined, the pharmacokinetics (PK) of 765IGF-MTX will be assessed on days 1 and 2 and days 15 and 16 of cycle 1 at the MTD in three patients.

Study Schema

Pharmacodynamic samples on day 1 of cycle 1, days 1 and 15 of cycle 2, and day 15 of cycles 4 and 6 before 765IGF-MTX administration.

At the MTD: Pharmacokinetic samples starting on day 1 (including time points on day 2), and day 15 (including time points on day 16) of cycle 1

Dose Finding Component: 1 cycle = 28 days

day	Cycle 1			Cycle 2			Cycle 3 and beyond ²					
	1	8	15		1	8	15		1	8	15	
765IGF-MTX*	X	X	X		X	X	X		X	X ¹	X ¹	
Clinic visit	X	X	X		X	X	X		X	X ¹	X ¹	

* at assigned dose level (see table below)

¹Day 8 and day 15 visits at physician's discretion cycle 3 and beyond

²Treatment continues until disease progression, unacceptable toxicity, patient refusal or other reason as found in section 7.11

Phase I Dose Levels

Dose Level	765IGF-MTX Dose	Number of Patients*
1	0.20 µequivalents per kg	1-9
2	0.40 µequivalents per kg	1-9
3	0.80 µequivalents per kg	1-9
4	1.6 µequivalents per kg	1-9
5	2.5 µequivalents per kg	1-9

*dose escalation cohorts between 1-9 patients; total of 9 patients in MTD cohort. At the discretion of the principal investigator, intra-patient dose escalation between cycles is also allowed but only after 2 cycles at the assigned dose level and confirmation of safety in at least 3 patients treated at the higher dose level.

Abbreviations

Abbreviation	Definition
AE	adverse event
ALT	alanine aminotransferase
AML	acute myelogenous leukemia
ANC	absolute neutrophil count
AST	aspartate aminotransferase
BM	bone marrow
CIR	Cumulative Incidence of Relapse rate
cm	centimeter
CR	complete remission
CRI	Compete remission with incomplete hematologic recovery (same as "marrow CR")
CMMI	Chronic myelomonocytic leukemia
CTCAE	(NCI) Common Terminology Criteria for Adverse Events
CTEP	Cancer Therapy Evaluation Program
dL	deciliter
DFS	time to relapse
DLT	dose-limiting toxicity
ECOG	Eastern Cooperative Oncology Group
EGFR	epidermal growth factor receptor
EFS	Event-Free Response
FDA	Food and Drug Administration
h	hour
HL	Hodgkin Lymphoma
IC50	50% Inhibitory Concentration, the concentration needed to inhibit cell growth by 50%
IGF-1	insulin-like growth factor-1
IGF-1R	insulin-like growth factor-1 receptor
IHC	immunohistochemistry
IND	Investigational New Drug
IRB	institutional review board
kg	kilogram
lb	pound
mg	milligram
min	minute
mL	milliliter
mm ³	cubic millimeters
MDS	myelodysplastic syndrome
MTD	maximum tolerated dose
MTX	methotrexate
NCI	National Cancer Institute
O-AML	Oligoblastic acute myelogenous leukemia
ORR	Overall response rate (= CR rate + CRI rate + PR rate)
OS	Overall Survival rate
PK	Pharmacokinetics studies
PD	Pharmacodynamics studies
PFS	Progression free survival (Time to disease progression or death from MDS, O-AML, or CMML)

PO	per os (by mouth)
PR	Partial Remission
RFS	Relapse-Free Survival
SAE	serious adverse event
US	United States
VEGF	vascular endothelial growth factor
wt	weight

1. Introduction

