Hypoglycemia in the higher dose groups was an exaggerated pharmacological effect of IGF, which was mitigated by the use of 5% dextrose as a vehicle for delivery of 765IGF-MTX conjugate. The pathogenesis of the anaphylactoid reactions was not clear, but may have been caused by either methotrexate, IGF or the combination thereof. Vomiting, diarrhea, anorexia and weight loss are known reactions to methotrexate.

The highest non-severely toxic dose in beagles was 0.5 $\mu\text{eq}/\text{kg}$. Using the conversion from doses in dogs in $\mu\text{Eq}/\text{kg}$ to equivalent human dose in $\mu\text{Eq}/\text{kg}$, the equivalent human dose to 0.5 $\mu\text{Eq}/\text{kg}$ in dogs is 0.27 $\mu\text{Eq}/\text{kg}$ in humans^{42,43}.

IGF-MTX does not cause significant cytopenia

Cytopenia is a particular concern for MDS, CMML, and O-AML since it is a principal sequela of these diseases. In both rat and dog repeat dose GLP toxicology testing IGF-MTX caused almost no cytopenia, even at the highest doses tested. In both rat and dog toxicology studies IGF-MTX caused a slight dose-dependent reduction in erythrocyte mass, but even at the highest doses tested erythrocyte mass was within normal ranges. In rats but not dogs neutrophils were also slightly decreased by IGF-MTX but remained within normal ranges even at the highest doses. No other hematological parameters were affected by IGF-MTX.

In the completed Phase I dose-escalation study in human solid tumor patients, a dose of 0.8 $\mu\text{Eq}/\text{kg}$ was found to be tolerated without any serious adverse events. Since MDS patients have greater cytopenia than solid tumor patients, and for safety of MDS patients, we are conducting a new dose escalation in this study beginning at a dose level of 0.2 $\mu\text{Eq}/\text{kg}$ administered on days 1, 8, and 15. See the schema on page 6 for the dose escalation schema.

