11.2. Adverse Event Documentation

Adverse events occurring from the first dose of 765IGF-MTX up to and including 30 days after administration of the last dose must be documented. Adverse events attributed to a study-related procedure which occur prior to the initiation of study treatment must be documented as well.

For the purposes of this study, adverse event documentation requirements will be determined based on grade, expectedness and relationship to study therapy as follows:

	Grade 1	Grade 2		Grade 3		Grade 4 and 5
	Expected or Unexpected	Expected	Un-expected	Expected	Un-expected	Expected or Unexpected
Unrelated	Not required	Not required	Not required	Not required	Required	Required

Possible						
Probable						
Definite	Not required	Required	Required	Required	Required	Required

All patients will be monitored with appropriate event documentation in EDC Easy® through the final study visit per section 7 as it is expected that most treatment related adverse events will occur during this period.

However, all toxicities (grades 1, 2, 3, 4, 5) must be reported within internal study forms, and include the following descriptors:

- Toxicity
- Grade
- Date
- Expected or Unexpected
- Attribution (unrelated, unlikely, possible, probably, definite)

For grade 2 or higher toxicities, principal investigator and/or treating physician will be notified the same day as study visit.

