13.2.1. Efficacy Endpoints

The numbers of overall complete remissions (patients with a best objective response of CR or CRi), and overall remissions (patients with a best objective response of CR, CRi or PR) will be summarized by observed rates and estimated 95% CIs. If there are sufficient numbers of patients achieving remissions for an analysis to be informative, logistic regression will be used to model the probability of achieving a remission as a function of the assigned 765IGF-MTX dose level for Cycle 1. Other factors may be added to the model to investigate their prognostic value in predicting remission.

In general, missing values will not be replaced by imputed values. Patients who, for any reason, do not supply bone marrow for response assessment are counted among those not achieving a response.

Kaplan-Meier time-to-event analyses will be conducted on overall survival and progression-free survival. Mortality (all causes) at certain landmark time points (e.g., 90 and 180 days) will also be estimated together with 95% CIs. Cox proportional hazards models will be fit to these time-to-event endpoints with the assigned 765IGF-MTX dose level for Cycle 1 serving as the independent variable in the model.

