Appendix I – Response Criteria for Acute Leukemia

Acute Myeloid Leukemia⁴⁵

Table 5. Response criteria in AML

Category	Definition
Complete remission (CR)*	Bone marrow blasts < 5%; absence of blasts with Auer rods; absence of extramedullary disease; absolute neutrophil count $> 1.0 \times 10^9/L$ (1000/ μ L); platelet count $> 100 \times 10^9/L$ (100 000/ μ L); independence of red cell transfusions
CR with incomplete recovery (CRI)†	All CR criteria except for residual neutropenia ($< 1.0 \times 10^9/L$ [1000/ μ L]) or thrombocytopenia ($< 100 \times 10^9/L$ [100 000/ μ L])
Morphologic leukemia-free state‡	Bone marrow blasts < 5%; absence of blasts with Auer rods; absence of extramedullary disease; no hematologic recovery required
Partial remission (PR)	Relevant in the setting of phase 1 and 2 clinical trials only; all hematologic criteria of CR; decrease of bone marrow blast percentage to 5% to 25%; and decrease of pretreatment bone marrow blast percentage by at least 50%
Cytogenetic CR (CRC)§	Reversion to a normal karyotype at the time of morphologic CR (or CRI) in cases with an abnormal karyotype at the time of diagnosis; based on the evaluation of 20 metaphase cells from bone marrow
Molecular CR (CRM)¶	No standard definition; depends on molecular target
Treatment failure	
Resistant disease (RD)	Failure to achieve CR or CRI (general practice; phase 2/3 trials), or failure to achieve CR, CRI, or PR (phase 1 trials); only includes patients surviving ≥ 7 days following completion of initial treatment, with evidence of persistent leukemia by blood and/or bone marrow examination
Death in aplasia	Deaths occurring ≥ 7 days following completion of initial treatment while cytopenic; with an aplastic or hypoplastic bone marrow obtained within 7 days of death, without evidence of persistent leukemia
Death from indeterminate cause	Deaths occurring before completion of therapy, or < 7 days following its completion; or deaths occurring ≥ 7 days following completion of initial therapy with no blasts in the blood, but no bone marrow examination available
Relapse	Bone marrow blasts $\geq 5\%$; or reappearance of blasts in the blood; or development of extramedullary disease

Table 6. Outcome measures in AML

Category	Definition
Overall survival	Defined for all patients of a trial; measured from the date of entry into a study to the date of death from any cause; patients not known to have died at last follow-up are censored on the date they were last known to be alive

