Relapse-free survival*	Defined only for patients achieving CR or CRI;‡ measured from the date of achievement of a remission until the date of relapse or death from any cause; patients not known to have relapsed or died at last follow-up are censored on the date they were last examined
Event-free survival	Defined for all patients of a trial; measured from the date of entry into a study to the date of induction treatment failure, or relapse from CR or CRI;‡ or death from any cause; patients not known to have any of these events are censored on the date they were last examined
Cumulative incidence of relapse (CIR)†	Defined for all patients achieving CR or CRI;‡ measured from the date of achievement of a remission until the date of relapse; patients not known to have relapsed are censored on the date they were last examined; patients who died without relapse are counted as a competing cause of failure

*Relapse-free and disease-free survival have been used with the same definition

†It is important to provide estimates of cumulative incidence of death (CID) as well, since just considering the results of CIR may be misleading if for instance CIR is lower for one group but CID is actually higher for that same group.

‡In studies where the criterion CRI is used, relapse-free survival should be defined for all patients achieving CR or CRI; for event-free survival, relapse should be considered from CR and CRI.

FAILURE - aplasia Aplasia: Patient survives \geq 7 days following completion of initial treatment course then dies while cytopenic, with the last post-induction bone marrow aplastic or hypoplastic (i.e. < 20% cellularity) and without leukemia blasts.

FAILURE - indeterminate Indeterminate: (a) Patient survives < 7 days after completion of initial treatment course; **or** (b) patient survives \geq 7 days following completion of initial treatment course then dies with no persistent leukemia in the peripheral smear but no post-induction bone marrow examination.

RELAPSE FROM CR Relapse: Reappearance of leukemia blasts in the peripheral blood; or > 5% blasts in the bone marrow not attributable to another cause (e.g., recovery of normal cells following chemotherapy-induced aplasia); or appearance or reappearance of extramedullary disease.

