Appendix II – Response Criteria for MDS⁴⁷

Table 3. Proposed modified International Working Group response criteria for altering natural history of MDS⁷

Category	Response criteria (responses must last at least 4 wk)
Complete remission	
Bone marrow: $\leq 5\%$ myeloblasts with normal maturation of all cell lines*
 
Persistent dysplasia will be noted*†
 
Peripheral blood‡
 
Hgb ≥ 11 g/dL
 
Platelets $\geq 100 \times 10^9/L$
 
Neutrophils $\geq 1.0 \times 10^9/L$†
 
Blasts 0%

Partial remission	
All CR criteria if abnormal before treatment except:
 
Bone marrow blasts decreased by $\geq 50\%$ over pretreatment but still $> 5\%$
 
Cellularity and morphology not relevant

Marrow CR†	
Bone marrow: $\leq 5\%$ myeloblasts and decrease by $\geq 50\%$ over pretreatment†
 
Peripheral blood: if HI responses, they will be noted in addition to marrow CR†

Stable disease	Failure to achieve at least PR, but no evidence of progression for > 8 wks
Failure	Death during treatment or disease progression characterized by worsening of cytopenias, increase in percentage of bone marrow blasts, or progression to a more advanced MDS FAB subtype than pretreatment
Relapse after CR or PR	
At least 1 of the following:
 
Return to pretreatment bone marrow blast percentage
 
Decrement of $\geq 50\%$ from maximum remission/response levels in granulocytes or platelets
 
Reduction in Hgb concentration by ≥ 1.5 g/dL or transfusion dependence

Cytogenetic response	
Complete
 
Disappearance of the chromosomal abnormality without appearance of new ones
 
Partial
 
At least 50% reduction of the chromosomal abnormality

Disease progression	
For patients with:
 
Less than 5% blasts: $\geq 50\%$ increase in blasts to $> 5\%$ blasts
 
5%-10% blasts: $\geq 50\%$ increase to $> 10\%$ blasts
 
10%-20% blasts: $\geq 50\%$ increase to $> 20\%$ blasts
 
20%-30% blasts: $\geq 50\%$ increase to $> 30\%$ blasts
 
Any of the following:
 
At least 50% decrement from maximum remission/response in granulocytes or platelets
 
Reduction in Hgb by ≥ 2 g/dL
 
Transfusion dependence

Survival	
Endpoints:
 
Overall: death from any cause
 
Event free: failure or death from any cause
 
PFS: disease progression or death from MDS
 
DFS: time to relapse
 
Cause-specific death: death related to MDS

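### PFS counts only deaths from the disease but is analysed by Kaplan-Meier with no competing-risk method and no cause-of-death rule, so the curve lies at or above all-cause progression-free survival (minor)

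*Combined protocol and SAP*

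**What the plan says.** - **Event definition.** The Abbreviations list gives "Progression free survival (Time to disease progression or death from MDS, O-AML, or CMML"). The Survival row of Appendix II has the same form for MDS: "PFS: disease progression or death from MDS".
- **Analysis.** Section 13.2.1 states that "Kaplan-Meier time-to-event analyses will be conducted on overall survival and progression-free survival", and then that "Cox proportional hazards models will be fit to these time-to-event endpoints with the assigned 765IGF-MTX dose level for Cycle 1" as the covariate. It names no competing-risk method for PFS and does not say how a non-disease death before progression is handled.
- **Other endpoints.** Appendix I defines overall survival as "measured from the date of entry into a study to the date of death from any cause". Relapse-free survival there also counts any death. For cumulative incidence of relapse, "patients who died without relapse are counted as a competing cause of failure".
- **Cause of death.** Section 11.2 records "Attribution (unrelated, unlikely, possible, probably, definite"), and Section 11.4 asks about association with the study drug. Section 12.3 mentions deaths due to disease but gives no criterion.
- **Status of PFS.** It is absent from Sections 2.2 and 3.2 and from the body of 13.4.1. It remains in the contents entry for 13.4.1 and in Section 13.2.1.

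**The concern.** A reader takes a PFS curve as the probability of being alive and free of progression. Kaplan-Meier applied to this event does not estimate that whenever someone dies of another cause before progressing. Nor is it one minus the cumulative incidence of the disease-specific event, because censoring treats the dead as if they could still progress.

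The curve also depends on an attribution that the plan leaves open. Section 1.2.1 says "Cytopenia is a particular concern for MDS, CMML, and O-AML since it is a principal sequela of these diseases", so a death from infection or bleeding could be classed either way.

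The dose comparison is affected in meaning. The Cox model remains a valid cause-specific hazard analysis. However, a death attributed to drug toxicity would not count against the dose in the PFS analysis, although Section 10.1.9 warns of fatal methotrexate toxicities.

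**Working it through.** The plan gives no PFS figure to reproduce. The direction follows from algebra. The size needs assumptions.

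**Direction.** At each event time let n be the number at risk, d1 the progressions or disease deaths, and d2 the other deaths. With other deaths censored, the Kaplan-Meier factor is 1 − d1/n. With all deaths counted, it is 1 − (d1 + d2)/n. The risk sets are the same, so the first factor is never smaller, and neither is the product. The curves coincide if no non-disease death precedes progression. In 20,000 simulated data sets (n = 5, 9, 20 and 45, with ties and censoring) the ordering was never violated.

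**Nine-patient illustration (invented data).** First events occur at months 1, 2, 2.5, 3, 4, 5, 6, 7 and 8. Those at months 2 and 5 are non-disease deaths. At month 5:
- all-cause: 3/9 = 33.3%
- as the plan defines it: (8/9)(6/7)(5/6)(4/5) = 50.8%

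**Size.** Assume constant independent hazards L1 (progression or disease death) and L2 (other death), with f = L2/(L1 + L2). The values of f are assumptions.
- Ratio of medians = 1/(1 − f).
- When all-cause PFS is 0.5, the Kaplan-Meier curve reads 0.5^(1 − f).
- Disease-specific cumulative incidence at that time = (1 − f) × 0.5.

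| f | Median ratio | Kaplan-Meier PFS | Excess over 50% | 1 − cumulative incidence | Gap to Kaplan-Meier |
|---|---|---|---|---|---|
| 10% | 1.11 | 53.6% | 3.6 points | 55.0% | 1.4 points |
| 20% | 1.25 | 57.4% | 7.4 points | 60.0% | 2.6 points |
| 30% | 1.43 | 61.6% | 11.6 points | 65.0% | 3.4 points |

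If the same deaths were all attributed to the disease, the curve would read 50%. Attribution alone can therefore move it by the 3.6 to 11.6 points shown.

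**At the plan's landmark times.** Section 13.2.1 names days 90 and 180 as examples for mortality. For assumed all-cause median PFS of 2, 4 or 6 months and f from 10% to 30%, the excess at those times is 2.5 to 12.9 points. With a 4-month median, all-cause PFS at day 180 is 35.9%, and the curve as defined reads 39.8%, 44.1% or 48.8%.

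**Against sampling error.** The table of Phase I dose levels allows at most 9 patients at each of 5 levels, so 5 × 9 = 45. Exact 95% intervals for a proportion near one half are 21% to 86% for 5 of 9 and 36% to 66% for 23 of 45. Both are wider than the bias.

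**The case against.** The strongest reply has four parts.

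1. **The definition is adopted, not accidental.** It follows the MDS criteria in Appendix II, and choosing a disease-specific event is a choice of estimand. That is fair. The fault lies in pairing the event with Kaplan-Meier under the name PFS, with no attribution rule.
2. **Censoring is inferred, and a full SAP is still to come.** Section 13 calls itself an overview and defers complete details to a SAP due before database lock. That SAP could settle the matter, but only by changing the event or the method. As written, Kaplan-Meier on this event leaves no other place for a non-disease death.
3. **Other text touches on disease-related events.** Sections 11.1 and 11.3 separate events due to the underlying disease. Appendix I has categories for death in aplasia and from indeterminate cause. Appendix II lists cause-specific death. None is tied to the PFS event, so the gap remains.
4. **Little depends on it.** PFS drives no decision, and Section 13.1 sizes nothing on it. Overall survival, relapse-free survival and landmark mortality count all deaths. Follow-up normally ends 30 days after the last dose (Section 7.11), which limits how many such deaths are seen. All of this stands and is why the point is minor. The assumed f has no support in the documents, so the figures are illustrations.

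**Conclusion.** The concern holds, as a minor point. Given that non-disease deaths are censored, which the definition and method imply but do not state, the ordering is certain: the curve is at or above all-cause PFS. The amount cannot be derived from the documents. Under constant independent hazards and an assumed 10% to 30% of first events being non-disease deaths, the excess is 3.6 to 11.6 points when all-cause PFS is 50%. With no such deaths there is no excess. The result also turns on an unspecified judgement about cause of death.

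**What to change.** First confirm that PFS is still to be analysed, since the objectives and endpoints no longer list it. If it is, make these changes in the Abbreviations list and Section 13.2.1:

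- Define PFS as time from study entry (the origin Appendix I uses for overall survival) to progression or death from any cause.
- Censor patients alive without progression at their last disease assessment.
- State which progression criteria apply to O-AML and CMML. Appendix I defines relapse and resistant disease but not progression. Section 3.2.2 lists no CMML criteria. Section 7.2.1 cites both appendices for all three diseases without allocating them.

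If the disease-specific event is kept, give it another name, state who attributes cause of death and by what criteria, and report its cumulative incidence with other deaths as a competing event, as Appendix I does for relapse.

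The cost is one definition line, one sentence in Section 13.2.1, and the progression criteria, which PFS needs under either definition. No patient procedure changes. There are two downsides. PFS may look slightly shorter, and it departs from the Appendix II wording. Ascertainment also stays uneven: after the 30-day visit, disease assessment continues only for patients who leave treatment in response (Section 8.1, footnote 1), so later deaths count only as far as survival follow-up captures them.
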